## 9.5. Evaluation of Severity and Causality

### 9.5.1. Evaluation of Severity

The severity of AEs (excluding local injection site reactions) will be graded according to the following scale:

- **Mild:** Does not interfere in a significant manner with the patient's normal functioning level. It may be an annoyance. Prescription drugs are not ordinarily needed for relief of symptoms, but may be given because of personality of the patient.
- **Moderate:** Produces some impairment of functioning but is not hazardous to health. It is uncomfortable or an embarrassment. Treatment for symptom may be needed.
- Severe: Produces significant impairment of functioning or incapacitation and is a definite hazard to the patient's health. Treatment for symptom may be given and/or patient hospitalized.

If a laboratory value is considered an AE, its severity should be based on the degree of physiological impairment the value indicates.

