### Local Injection Site Reactions

The severity of local injection site reactions will be graded by the investigator using a 4-point scale (mild, moderate, severe, or very severe), adapted from the toxicity grading scale table from the Food and Drug Administration Draft Guidance for Industry: Toxicity Grading Scale for Healthy Adult and Adolescent Volunteers Enrolled in Preventive Vaccine Clinical Trials dated April 2005. Local injection site reactions will be reported in detail as indicated on the CRF and/or SAE form, as appropriate.

The complete severity grading scale for assessing local injection site reactions is provided in Appendix 3.

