### Analysis

All AEs reported in this study will be coded using the currently available version of the Medical Dictionary for Regulatory Activities (MedDRA®). Coding will be to lowest level terms. The verbatim text, the preferred term (PT), and the primary system organ class (SOC) will be listed.

Summaries of all TEAEs by treatment group will include:

- The number (n) and percentage (%) of patients with at least 1 TEAE by SOC and PT
- TEAEs by severity (according to the grading scale outlined in Section 9.5.1), presented by SOC and PT
- TEAEs by relationship to treatment (related, not related), presented by SOC and PT
- Treatment-emergent AESIs (defined with a PT or a prespecified grouping). If any signal is detected with any AESI which warrants further characterization, the time-to event approach (Kaplan-Meier methodology) will be used. Time from the first dose of study drug to the first occurrence of the event will be calculated (only the first event will be counted). Patients without any event will be censored at the end of the TEAE period. Incidence rates at 6, 12, 24, 36, and 48 months of exposure will be presented and Kaplan-Meier curves will be provided.
- Drug-induced liver injury (namely ALT, AST, alkaline phosphatase and total bilirubin). The proportion of patients with potentially clinically significant abnormality values at any post-baseline visit by baseline status will be displayed for each parameter. A graph of distribution of peak values of ALT versus peak values of total bilirubin will also be presented. The ALT and total bilirubin values will be presented on a logarithmic scale. The graph will be divided into 2 quadrants with a vertical line corresponding to 3 x ULN for ALT and a horizontal line corresponding to 2 x ULN for total bilirubin.

Deaths and other SAEs will be listed and summarized by treatment group.

Treatment-emergent adverse events leading to permanent treatment discontinuation will be listed and summarized by treatment group.

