# APPENDIX 2. SUMMARY OF TLC DIET FOR HIGH CHOLESTEROL

Total Fat	25% - 35% total calories*		
Saturated fat*	<7% total calories		
Polyunsaturated fat	up to 10% total calories		
Monounsaturated fat	up to 20% total calories		
Carbohydrates †	50% - 60% total calories*		
Protein	~15% total calories		
Cholesterol	<200 mg/day (5.172 mmol/day)		
Plant Sterols	2g		
Soluble Fiber such as psyllium	10g - 25g		

\* ATP III allows an increase of total fat to 35 percent of total calories and a reduction in carbohydrate to 50 percent for persons with the metabolic syndrome. Any increase in fat intake should be in the form of either polyunsaturated or monounsaturated fat. Trans-fatty acids are another LDL-raising fat that should be kept at a low intake.

† Carbohydrate should derive predominantly from foods rich in complex carbohydrates including grains—especially whole grains—fruits, and vegetables.

APPENDIX 3.	ASSESSMENT OF LOCAL INJECTION SITE
	REACTIONS

Reaction to Injectable Product	Mild (Grade 1)	Moderate (Grade 2)	Severe (Grade 3)	Very Severe (Grade 4)
Pain	Does not interfere with activity	Interferes with activity or repeated use of non-narcotic pain reliever	Prevents daily activity or repeated use of narcotic pain reliever	Emergency Room (ER) visit or hospitalization
Tenderness	Mild pain to touch	Pain with movement	Significant pain at rest	ER visit or hospitalization
Erythema / Redness *	2.5 – 5 cm	5.1 – 10 cm	>10 cm	Necrosis or exfoliative dermatitis
Swelling **	2.5 – 5 cm and does not interfere with activity	5.1 – 10 cm or interferes with activity	> 10 cm or prevents daily activity	Necrosis
Itching	Does not interfere with activity	Interferes with activity or repeated use of topical or systemic treatment	Prevents daily activity or leads to other significant dermatologic conditions (such as infection, scarring, etc.)	Emergency Room (ER) visit or hospitalization
Other (Please specify)***	No modification of daily activities and/or does not require symptomatic treatment.	Hinders normal daily activities and/or requires symptomatic treatment.	Prevents daily activities and requires symptomatic treatment.	Emergency Room (ER) visit or hospitalization

\* In addition to grading the measured local reaction at the greatest single diameter, the measurement should be recorded as a continuous variable.

\*\* Swelling should be evaluated and graded using the functional scale as well as the actual measurement.

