- All TEAEs regardless of relationship in one column and, in the same table a second column with TEAEs related to alirocumab according to investigator's opinion by primary SOC, HLGT, HLT and PT;
- All TEAEs by maximal severity (i.e., mild, moderate or severe), presented by primary SOC and PT, sorted as defined above;
- The event rate per patient-year (the number of patients with an event in question divided by total patient-years) will be provided for all TEAEs by SOC and PT. For a patient with event, patient year is censored at time of first event; for patient without event, it corresponds to length of TEAE period;
- Kaplan-Meier curves will be provided, when appropriate, for time from first dose of study treatment to the first occurrence of selected TEAEs as well as incidence

rates at 48, 96, 144, and 192 weeks of exposure. Patients without any event will be censored at the end of the TEAE period. Selected TEAEs could be AESIs (e.g neurocognitive events), or TEAE related to any clinically significant signal that needs further characterization;

The frequency of selected AEs by SOC and PT over time during the treatment period (number of patients experiencing AE and percentage by patient-months) will be provided, when appropriate, by time intervals defined as: ≤48 weeks, >48 to ≤96 weeks, >96 to ≤144 weeks, >144 to ≤192 weeks, using the PROC LIFETEST with the actuarial method. Only the first event will be counted.

Analysis of all treatment emergent serious adverse event(s)

- All serious TEAEs by primary SOC, HLGT, HLT, and PT and by SOC/PT; Patient listings of serious TEAEs will be provided for the report appendix.
- All serious TEAEs regardless of relationship in one column and in the same table a second column with TEAEs related to alirocumab according to investigator's opinion, by primary SOC, HLGT, HLT, and PT;
- The event rate per patient-year will be provided for all serious TEAEs by SOC and PT.

Analysis of all treatment-emergent adverse event(s) leading to treatment discontinuation

• All TEAEs leading to permanent treatment discontinuation, by primary SOC, HLGT, HLT, and PT and by SOC/PT; Patient listings of TEAEs leading to permanent treatment discontinuation will be provided for the report appendix.

Analysis of groupings of adverse events including selected adverse events of special interest

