- All grouping of TEAEs including adverse events of special interest, as listed in Section 4.7.1.2, will be presented by SMQ/CMQ and PT (when selection is based on SMQs/CMQs) and by SOC and PT (when selection is based on the e-CRF tick box or HLGT/HLT). The summaries will be sorted by decreasing incidence of PT within each SOC/SMQ (in the PRALUENT group).
- Neurocognitive events adjudicated by the neurocognitive events review committee will also be summarized by primary SOC and PT. They will also be summarized according to the adjudication of possible etiology of the neurocognitive events (Yes/No) (Section 4.7.1.2).
- All TEAEs within diabetes grouping will be analyzed overall and according to the diabetic status at baseline.
The following variables will also be tabulated for the local injection site reactions TEAEs:

- Intensity of the event (mild, moderate, severe);
- Number of events divided by the number of study treatment injections received;
- Time from first study treatment injection to first injection site reaction;
- Description of the highest intensity of each symptom recorded in the specific e-CRF page with table and bar chart.

Description of symptoms and possible etiologies for General Allergic Reaction TEAE reported by investigator (using the tick box), will be presented.

Post-treatment adverse events

- All post-treatment AEs by primary SOC and PT, sorted by the internationally agreed SOC order and decreasing incidence of PTs (in the PRALUENT group) within each SOC;
- All post-treatment SAEs by primary SOC and PT, sorted by the sorting order defined above.

Subgroup of patients with two consecutive LDL-C <25 mg/dL (<0.65 mmol/L)

If applicable, similar summaries of TEAEs as those described above will be provided on the safety subgroup population of patients with two consecutive results of LDL-C <25 mg/dL (as defined in Section 4.8) in both patient groups. Only TEAEs for which it will be confirmed or unclear that they occurred, worsened or became serious on the day or after the day the first level of LDL-C <25 mg/dL was observed will be considered in this summary.

In addition, the neurocognitive event rate in patients with 2 consecutive results separated by at least 21 days for calculated LDL-C <25 mg/dL, and calculated LDL-C <15 mg/dL, will be assessed.

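### SAP 5.7.1 tabulates local injection site reactions on three severity levels although the protocol grades them on four, so a very severe reaction has no category in two planned tables

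*SAP*

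**What the plan says.** The protocol has two severity scales. The three-level scale in Section 9.5.1 opens with an exclusion: "The severity of AEs (excluding local injection site reactions) will be graded according to the following scale". For the excluded events, the subsection on local injection site reactions says they are "graded by the investigator using a 4-point scale (mild, moderate, severe, or very severe", and it points to Appendix 3, whose last column is headed "Very Severe (Grade 4". The statistical section, 10.4.4.1, then plans "TEAEs by severity (according to the grading scale outlined in Section 9.5.1), presented by SOC and PT".

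SAP 5.7.1 has three displays that bear on the severity of these reactions:

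- For local injection site reaction TEAEs: "Intensity of the event (mild, moderate, severe".
- For all TEAEs together: "All TEAEs by maximal severity (i.e., mild, moderate or severe), presented by primary SOC and PT".
- A table and bar chart of the highest intensity of each reaction symptom, with no levels named.

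SAP 1.2.3, which lists modifications from the protocol's statistical section, mentions only that all analyses become descriptive after the early termination.

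**The concern.** The SAP applies to injection site reactions the scale that the protocol says does not apply to them. The missing level is the top one. In Appendix 3 it covers necrosis, exfoliative dermatitis, and reactions that lead to an emergency room visit or a hospital stay. SAP 4.7.1.2 lists local injection site reactions as an AESI, and AESIs are among the events to be described under the primary endpoint. In a single-arm study whose output is descriptive safety tables, the categories of a table largely decide what a reader can learn from it. A table that cannot show the worst grade could be read as evidence that there were no such reactions.

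**Working it through.** No arithmetic beyond a count of levels applies. The relevant places, side by side:

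| Place | Events covered | Levels named |
|---|---|---|
| Protocol 9.5.1, general scale | AEs other than local injection site reactions | 3 |
| Protocol 9.5.1, Local Injection Site Reactions | Local injection site reactions | 4 |
| Protocol Appendix 3 | Each reaction symptom (pain, tenderness, erythema, swelling, itching, other) | 4 |
| Protocol 10.4.4.1 | TEAEs by severity | Refers back to 9.5.1 |
| SAP 5.7.1, reaction intensity | Local injection site reaction TEAEs | 3 |
| SAP 5.7.1, maximal severity | All TEAEs | 3 |
| SAP 5.7.1, highest intensity per symptom | Each reaction symptom | Not stated |

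1. *Are the SAP lists complete or only examples?* The maximal-severity item introduces its levels with i.e., so that list is complete. The reaction-intensity item gives the same three levels with nothing to suggest a further one.
2. *Does the SAP map Grade 4 elsewhere?* No. The term very severe does not occur in the SAP, and no rule combines Grades 3 and 4.
3. *Is the change declared?* No. SAP 1.2.3 is silent on the severity scale.
4. *Could Protocol 10.4.4.1 mean only the three-level scale, since it speaks of one grading scale?* That reading does not help, because the three-level scale excludes these reactions. Either the reference to 9.5.1 takes in the four-level scale, or these reactions have no grade in the severity table at all.
5. *What happens to one patient?* SAP 5.7.1 takes the worst severity when a patient has several instances of the same event. If the worst is very severe, neither table that names its levels has a place for it. The patient could be omitted, left uncategorised or merged into severe, and the SAP does not say which.
6. *Does the symptom display repair this?* Only in part. It may show Grade 4 because its levels are not capped, but it describes symptoms one by one. It does not give the number of patients by overall event intensity.

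**The case against.** The best reply is that little is lost. The primary endpoint is the incidence of AEs, not their severity. A very severe reaction is still counted in the all-TEAE tables, in the AESI grouping and in events per injection. If it is serious, it also appears in the serious TEAE tables and listings; if it leads to permanent discontinuation, it appears there too. The symptom display follows the structure of Appendix 3, which grades symptom by symptom and gives no rule for a single event grade. All of this stands, and it limits the point to two descriptive tables.

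It does not remove the point. The serious TEAE tables as described do not show intensity, and Grade 4 is not the same as serious. Protocol 9.3.2 counts an emergency room or hospital admission as hospitalization only beyond 24 hours, while in Appendix 3 any emergency room visit for pain, tenderness or itching is Grade 4. A short visit can therefore be Grade 4 without meeting that criterion, unless it is judged serious on another ground.

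A reader might infer three stronger things that the documents do not support:

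- *That every Grade 4 reaction will be lost or misgraded.* This depends on the CRF, which is not among the documents. The event-level field may hold three levels or four, and a programmer may add a row.
- *That the problem can be sized from the planned number of injections.* SAP 1.1 records that the study was terminated early on January 31, 2020, the enrolment of about 1600 is only an expectation, and no document gives a Grade 4 rate.
- *That the protocol treats every local reaction as an AESI.* Protocol 9.4.3 includes only reactions that are allergic in nature and need another physician's evaluation. The broader listing is the SAP's.

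**Conclusion.** The conflict is explicit, and nothing in the SAP resolves it: four levels in the protocol, three in the two SAP displays that name their levels, with no mapping rule and no declared departure from Protocol 10.4.4.1. Taken literally, a very severe reaction has no category in either table. The consequence is confined to descriptive severity reporting. No test, sample size or incidence figure is affected, and the number of reactions concerned cannot be estimated from the documents. The conclusion rests on reading the SAP as written. What would happen to a Grade 4 record in practice remains unknown without the CRF and the table shells. The text should be corrected, because as it stands it contradicts the protocol on the most severe category of a listed AESI.

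**What to change.** In SAP 5.7.1:

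- List injection site reaction intensity as mild, moderate, severe and very severe.
- In the table of all TEAEs by maximal severity, add a very severe level that applies to these reactions only, or a footnote that sends the reader to the four-level table.
- Name the same four levels for the display of highest intensity per symptom.

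First check which levels the event-level CRF field holds. If it holds only three, an added row would stay empty. The SAP should then either derive the event grade as the worst Appendix 3 symptom grade, or state that Grades 3 and 4 are combined and report the Grade 4 count separately. Whichever route is taken, any remaining departure from Protocol 10.4.4.1 belongs in SAP 1.2.3.

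If the event-level field already has four levels, the cost is a line or two of SAP text and one extra row in each table. If it does not, a short derivation from the symptom grades, which the protocol already requires, is added.

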4.7.1. Adverse Events Variables

The period of safety observation starts from the time when the patient gives informed consent and continues into the following periods:

- The PRE-TREATMENT period: defined as the time from the signed informed consent up to the first study treatment injection.
- The treatment-emergent adverse event (TEAE) period: defined as the time from the first dose of study drug to the last study visit.
- The POST-TREATMENT period: defined as starting the day after the end of the TEAE periods up to the patient's end of study.

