4.8. Other Variables

The other endpoints of the study will include:

- The percent change in hs-CRP from baseline to protocol specified visits. Hs-CRP values greater or equal to 10 mg/L will be excluded from analyses in a second approach, since these are suggestive of concurrent infection(1). PCSA (potentially clinically significant abnormalities) criteria for hs-CRP are listed in Appendix 10.2.
- The absolute change in HbA1c (%) from baseline to protocol specified visits. PCSA criteria for HbA1c are listed in Appendix 10.2.
- The proportion of patients with two consecutives results, separated by at least 21 days, of calculated LDL-C <25 mg/dL (<0.65 mmol/L) (and again for calculated LDL-C <15 mg/dL [< 0.39 mmol/L]) during the treatment period.
- For the patients with two consecutive results as described above, the time to the first calculated LDL-C <25 mg/dL (<0.65 mmol/L) (and again for calculated LDL-C <15 mg/dL [< 0.39 mmol/L]) during the treatment period.

Protocol schedule visits will be assigned to the Analysis Windows (See Appendix 10.1).

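### In the very-low-LDL-C subgroup, events count from the first low value, but the only person-time the SAP defines starts at first dose, so a per-patient-year rate produced as written would be too low

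*SAP*

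**What the plan says.** SAP 4.8 defines the group through this endpoint: "The proportion of patients with two consecutives results, separated by at least 21 days, of calculated LDL-C <25 mg/dL", during the treatment period. The same is done at 15 mg/dL.

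SAP 5.7.1 then says that, if applicable, "similar summaries of TEAEs as those described above will be provided on the safety subgroup population of patients with two consecutive results". Within that summary it keeps only TEAEs confirmed to have, or that may have, "occurred, worsened or became serious on the day or after the day the first level of LDL-C <25 mg/dL was observed".

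The summaries earlier in SAP 5.7.1 include an event rate per patient-year, for all TEAEs and for serious TEAEs. It is defined as "the number of patients with an event in question divided by total patient-years". Time stops at the first event for a patient who has one; "for patient without event, it corresponds to length of TEAE period". SAP 4.7.1 gives that period as "defined as the time from the first dose of study drug to the last study visit". The Kaplan-Meier curves, made when appropriate, use "time from first dose of study treatment to the first occurrence of selected TEAEs".

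A further sentence in SAP 5.7.1 adds "the neurocognitive event rate in patients with 2 consecutive results separated by at least 21 days for calculated LDL-C <25 mg/dL", and likewise for 15 mg/dL. It gives no onset rule, time window or denominator.

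**The concern.** A rate is interpretable only if its events and its person-time cover the same interval. In this subgroup the events start at the first low LDL-C value. The only person-time rule in the SAP starts at the first dose of the extension. The weeks between the two dates add time but can add no events, so the rate is pulled down, which is the reassuring direction. The Kaplan-Meier curve has the related fault: it is flat by construction until the first low value, so its estimate at a given week covers less time at risk than its label says.

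At stake is the description of safety at confirmed very low LDL-C. The neurocognitive figures also raise a question of consistency. Those made under the AESI summaries take on the onset rule, whereas the added rates state none. Two neurocognitive figures for the same subgroup could then rest on different events.

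**Working it through.** The documents state no rate, event count or size for this subgroup, so there is no figure of the plan to reproduce. The check traces the definitions and then sizes the mismatch.

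**Does any passage restart the clock?** The sections that bear on it are SAP 4.7.1, 4.8, 5.7.1 and 5.8. SAP 4.8 and 5.8 deal with the time to the first low value, not with time after it. SAP 5.7.1 sets the onset rule for events but gives no matching start for person-time. The start for a patient with an event is not written out; first dose follows from the definition of the TEAE period.

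**Inputs**
- f, the week of the first low value. Protocol 7.2 allows no lipid profile before week 8, and the next scheduled LDL-C in Protocol Table 1 is at week 24. Assumed: f = 8 or 24.
- T, the end of the TEAE period. Planned follow-up is about 192 weeks, but SAP 1.1 records early termination and gives no distribution of follow-up. Assumed: T = 192 or 96.
- L, a constant hazard of first event after the low value. Assumed: 0.05 or 0.30 per year.

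**Formulas.** For rare events almost every patient contributes T weeks instead of T − f, so the shortfall is about f/T. In general, with f and T in years (52.18 weeks per year):

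- P = 1 − exp(−L(T − f)) is the expected number of first events per patient.
- Person-time from the low value is P/L; from first dose it is f + P/L.
- The rate as written is P/(f + P/L), so the relative shortfall is Lf/(Lf + P).

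Example, L = 0.05, f = 8 weeks (0.153 years), T = 192 weeks: T − f = 184 weeks = 3.526 years; P = 1 − exp(−0.1763) = 0.1617; Lf = 0.0077; shortfall = 0.0077/(0.0077 + 0.1617) = 4.5%.

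| T (weeks) | f (weeks) | f/T | L = 0.05 | L = 0.30 |
|---|---|---|---|---|
| 192 | 8 | 8/192 = 4.2% | 4.5% | 6.6% |
| 192 | 24 | 24/192 = 12.5% | 13.4% | 18.2% |
| 96 | 8 | 8/96 = 8.3% | 8.7% | 10.4% |
| 96 | 24 | 24/96 = 25.0% | 25.6% | 28.9% |

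**Simulation.** With a true rate of 2.0 per 100 patient-years, person-time from first dose gave 1.91 and 1.75 (T = 192; f = 8, 24) and 1.84 and 1.49 (T = 96). Person-time from the first low value gave 1.99 to 2.01 in every case.

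**Kaplan-Meier.** With f = 24, an incidence labelled 48 weeks reflects 48 − 24 = 24 weeks in which an event could count.

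**Added neurocognitive rates.** If events and person-time both cover the whole TEAE period, a constant hazard L gives an expected rate of L whatever f and T are. No bias follows from the missing onset rule alone.

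**The case against.** The strongest reply is that the mismatch is inferred. The subgroup summaries are conditional and need only resemble the earlier ones, and no subgroup rate formula is written, so a programmer could choose a matched denominator. That stands to this extent: the problem arises only if the rate or curve is produced. But the SAP supplies no other denominator, and following its stated rules gives the mismatched one.

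It may also be said that LDL-C was probably low in some patients before the first sample showed it, so the earlier weeks are relevant exposure. The mismatch remains, because events in those weeks are still excluded.

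The limits on consequence stand in full. The study is uncontrolled and everything is descriptive. SAP 1.1 also records that the question of prolonged very low LDL-C was removed from the risk management plan's missing information, and that this study was not expected to add to the safety profile.

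Two stronger readings are tempting and are not supported:
- A reader might infer that the added neurocognitive rates are inflated by events before the low value. The SAP does not say whether these rates are percentages or per patient-year. If whole-period events are set against whole-period time, the two match. What can be shown is inconsistency between two figures, not bias in a rate.
- A reader might infer that fatal-event rates are further understated, because a patient who dies between the two samples cannot qualify. The SAP plans no separate fatal-event rate; SAP 5.7.1.1 reports deaths as counts and percentages, and fatal TEAEs for the whole safety population.

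**Conclusion.** The point holds in a conditional form. If a per-patient-year rate is produced for this subgroup under the SAP's stated rules, it is too low by about f/T: 4% to 13% for 192 weeks of follow-up and 8% to 25% for 96 weeks, with the first low value at week 8 or 24. At 30 events per 100 patient-years the ranges are 7% to 18% and 10% to 29%. All these timings and event rates are assumptions; only the direction follows from the text. A Kaplan-Meier summary timed from first dose has the same fault of origin.

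The n (%) tables have no person-time denominator and so do not have this mismatch. No test and no primary-endpoint result is affected. The neurocognitive part is a matter of consistency. It merits a short change of SAP wording, no more.

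**What to change.** 1. For any per-patient-year rate or Kaplan-Meier summary in this subgroup, start time on the date from which SAP 5.7.1 counts events.
2. State which date that is: the first value below 25 mg/dL, as SAP 5.7.1 now reads, or the first of the qualifying pair, as in the time-to-event wording of SAP 5.8. Use it for numerator and denominator alike. Choosing the pair has a price: events after an earlier isolated low value drop out, including from the n (%) tables.
3. Apply the same onset rule and start date to the added neurocognitive rates, with a separate date for 25 and for 15 mg/dL, so that both neurocognitive figures for the 25 mg/dL subgroup rest on the same events. Say whether each is a percentage or a rate per patient-year.

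The cost is a few lines of SAP text, one or two derived dates, and slightly fewer person-years. No new data are needed.

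### In the LDL-C <25 mg/dL subgroup, SAP 5.7.1 counts adverse events from the first low value but inherits a patient-year rule that starts at first dose, so the subgroup rates per patient-year come out too low

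*SAP*

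**What the plan says.** SAP 4.8 defines the group through "The proportion of patients with two consecutives results, separated by at least 21 days, of calculated LDL-C <25 mg/dL" during the treatment period. SAP 5.7.1 then gives it its own adverse event output: "If applicable, similar summaries of TEAEs as those described above will be provided on the safety subgroup population of patients" who meet that definition, in both former treatment groups. The numerator has a special rule. Only TEAEs that certainly or possibly "occurred, worsened or became serious on the day or after the day the first level of LDL-C <25 mg/dL was observed will be considered" enter the table.

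The summaries listed earlier in 5.7.1 include rates per patient-year. For all TEAEs, a patient with an event contributes time up to the first event; "for patient without event, it corresponds to length of TEAE period". A second item says: "The event rate per patient-year will be provided for all serious TEAEs by SOC and PT". SAP 4.7.1 gives the TEAE period as "defined as the time from the first dose of study drug to the last study visit". Kaplan-Meier curves, where thought appropriate, are drawn "for time from first dose of study treatment to the first occurrence of selected TEAEs".

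The subgroup paragraph does not say when time at risk begins, and no other section does. Time to the first low LDL-C value appears in SAP 4.8 and 5.8, but only as an outcome in its own right. A further sentence in 5.7.1 asks for "the neurocognitive event rate in patients with 2 consecutive results separated by at least 21 days for calculated LDL-C <25 mg/dL", and the same below 15 mg/dL, with no window or denominator stated.

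**The concern.** The numerator and the denominator of the subgroup rate cover different periods. Weeks between first dose and the first low value count as time at risk, yet apart from events of unclear timing no event in those weeks can count. This is an immortal-time error. It concerns the counting windows only; it makes no claim about what LDL-C was before the first low sample.

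The error has one direction: the subgroup's rate per patient-year is pulled down, in a group that the SAP itself singles out for a safety look. Its size depends on when patients first have a low value, so the subgroup rate cannot be read against the all-patient rate, which has no such gap.

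**Working it through.** The plan states no figure to reproduce, so the check derives the size of the mismatch.

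**Inputs**
- Numerator window: from t0, the day of the first value below 25 mg/dL (SAP 5.7.1).
- Denominator window: from first dose to first event or last visit (SAP 5.7.1 with 4.7.1).
- t0: assumed 8 or 24 weeks. Week 8 is the first LDL-C assessment in the extension (SAP Figure 1 note). Week 24 is the next scheduled lipid sample, as none is planned at week 12 (Protocol Table 1).
- T: 192 weeks as planned (SAP 2.1). The sponsor stopped the study early (SAP 1.1), so actual follow-up may be shorter. T = 96 is used as an illustration only.

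**Patient-year rate.** Let D be the number of patients with a counted event, and x the time from first dose to that event or to the end of the TEAE period.
- As written: D / Σx.
- Matched windows: D / Σ(x − t0).
- Relative shortfall: 1 − Σ(x − t0)/Σx = Σt0/Σx, which is t0 divided by mean x when t0 is common to all.
- Because x cannot exceed T, the shortfall is at least t0/T. Events of unclear timing are in D both ways and cancel.

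Ignoring censoring at first event: 8/192 = 4.2%; 24/192 = 12.5%; 8/96 = 8.3%; 24/96 = 25.0%.

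With censoring at first event and a constant rate h per year after t0 (52.18 weeks per year), the mean years at risk after t0 are P = (1 − exp(−h(T − t0)/52.18))/h, and the shortfall is 1 − P/(t0/52.18 + P). For h = 0.02, t0 = 8, T = 192: P = 3.405, t0/52.18 = 0.153, and 0.153/3.558 = 4.3%.

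| t0, T (weeks) | t0/T | 2 per 100 patient-years | 50 per 100 patient-years |
|---|---|---|---|
| 8, 192 | 4.2% | 4.3% | 8.5% |
| 24, 192 | 12.5% | 12.9% | 22.3% |
| 8, 96 | 8.3% | 8.5% | 11.9% |
| 24, 96 | 25.0% | 25.3% | 31.6% |

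So at T = 192 a true rate of 2.00 per 100 patient-years would print as 2 × (1 − 0.043) = 1.91 or 2 × (1 − 0.129) = 1.74.

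The result does not depend on a common t0. In a simulation with t0 spread over weeks 8 to 96 and T over 60 to 192 weeks (mean t0 / mean T = 0.206), the shortfall ran from 20.8% when events were rare (2% over 96 weeks) to 29.8% when they were common (60% over 96 weeks).

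**Kaplan-Meier.** With a constant hazard λ after t0, the curve at week t is 1 − exp(−λ(t − t0)) as written and 1 − exp(−λt) if the clock restarts at t0. For uncommon events the shortfall is close to t0/t, not t0/T. With t0 = 24 and T = 96 it is about 50% at week 48 and 24.8% at week 96 when 2% have an event over 96 weeks. When 60% do, it is 17.2% at week 96, below t0/T = 25%. So t0/T is an approximation here and not a bound.

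**The case against.** The strongest reply is that the subgroup paragraph promises similar summaries, not identical ones, and only if applicable. It already overrides the main rules on which events count, so an analyst could reasonably move the start of time at risk as well. That room exists, and the dilution follows only if the inherited rule is applied as written. But the authors wrote a special numerator and no special denominator, and the only patient-year rule in the SAP starts at first dose. A programmer who follows the text will use it.

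Four stronger readings are tempting and are not supported.
- *Kaplan-Meier results are too low by at least t0/T.* The bound fails at late landmarks for common events. Part of the gap is also the choice of origin: if all patients shared one t0, delayed entry on the first-dose clock would leave the curve unchanged.
- *Follow-up ends at week 96, so 25% is the expected size.* SAP 5.7 and 5.8 do mention time points from week 8 to week 96, but the analysis windows in Appendix 10.1 and the Kaplan-Meier time points in 5.7.1 run to week 192. Early termination makes shorter follow-up plausible; no section gives its length.
- *The former placebo and former Praluent columns are diluted unequally.* This needs t0 to differ between them. If one column had t0 = 8 throughout and the other t0 = 24, equal true rates would differ by (184/192)/(168/192) = 1.10, or by (88/96)/(72/96) = 1.22 at T = 96. Nothing in the documents shows such a difference; both groups start at 75 mg every 2 weeks on the same lipid schedule.
- *The neurocognitive rates have the same error.* They have no restricted numerator. If events and time both cover the whole TEAE period, they match each other. They would differ in window from the neighbouring TEAE table, which is a matter of consistency and not a bias.

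It is also fair to say that little hangs on this. The analysis is descriptive and is not a protocol endpoint.

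**Conclusion.** The mismatch is in the text and nothing elsewhere in the SAP cures it. Applied as written, the subgroup rates per patient-year for all TEAEs and for serious TEAEs are too low by t0 over mean time at risk, and never by less than t0/T. At the planned 192 weeks t0/T is 4.2% to 12.5% for a first low value at week 8 or 24. If follow-up were 96 weeks, a figure the documents do not give, it would be 8.3% to 25.0%. Common events and later first low values push the shortfall higher. Both t0 and T are assumptions; the direction and the lower bound are not. A Kaplan-Meier curve for the subgroup would begin with a stretch almost free of events by construction.

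A reader might infer that the safety conclusions of the study are at risk. They are not: the n (%) tables, which carry the primary endpoint of adverse event incidence, do not use this denominator. This is a minor correction to a descriptive rate.

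**What to change.** In SAP 5.7.1, for this subgroup:
- start patient-years at the day of the first LDL-C value below 25 mg/dL;
- start any Kaplan-Meier curve on the same day, or keep the first-dose clock with delayed entry at that day;
- label the table as counted from the first low value.

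For consistency only, use the same kind of window for the neurocognitive rates, from the first value below 25 or below 15 mg/dL as relevant.

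The cost is one or two sentences and a changed start date in the subgroup programs. The LDL-C and event dates are collected already, and the date of the first low value is needed anyway for the time-to-event variable in SAP 4.8. The subgroup rate will rest on fewer patient-years. The change does not remove the selection that comes from requiring a second low value at least 21 days later: a patient who dies between the two samples never enters the subgroup. A footnote should say so.
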